5.6.3. Treatment Administration

Seborrheic dermatitis lesions that have completely resolved, in the opinion of the Investigator, do not require continued treatment. At every clinic visit the Investigator will determine if the IGA are considered ‘clear’ and the subject will stop applying the investigational product. The subject will contact the clinical study site and document in diary when seborrheic dermatitis returns prior to restarting investigational product. Subjects that clear between scheduled visits should return for an unscheduled visit for the Investigator to confirm IGA score are considered ‘clear’.

Unless otherwise instructed by the Investigator, subjects will apply investigational product once daily. At the Day 1 visit, the study staff will demonstrate to the subject how to apply ARQ-154 foam using the first Can from the Kit that is provided to the subject at Day 1. Study site staff will be trained to ensure a proper amount is dispensed from the foam Can and applied to seborrheic dermatitis lesion(s) as a thin layer and rubbed in thoroughly but gently, until the foam has disappeared. **For scalp lesions, special attention should be given to ensuring adequate investigational product is applied to scalp skin and not rubbed off on hair.** The subject will then practice dispensing a similar amount of investigational product and applying to seborrheic dermatitis lesion(s). The study staff will confirm that the subject’s application technique is correct. Cohort 1 Group 2 subjects will apply the last dose of IP for ARQ-154-116 Week 2 (Day 15) study visit; subjects will enroll in ARQ-154-214 on the same day but will start applying IP the following day (Day 2). The study staff will review with the subject the appropriate IP

dispensing and application technique for the ARQ-154-214 study during the Baseline visit (Day 1).

IP will be applied in the evening to areas of lesions of seborrheic dermatitis. IP will be applied at least 20 minutes before going to bed.

For Scalp Lesions: IP will be applied when the skin and hair on the scalp is dry. Subjects should dispense IP on their fingers, then part hair where there are lesions and rub IP into scalp skin. As the IP is applied, the subject should move any hair away to ensure that sufficient foam is actually applied directly to the affected skin on the scalp. Subjects should not use other hair products for at least an hour before or after application.

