6.5. Unscheduled Visit

Subjects that clear between scheduled visits should return for an unscheduled visit for the Investigator to confirm IGA score are considered 'clear' and subject will stop application of investigational product after Investigator confirmation. Subjects will call the site when seborrheic dermatitis returns prior to restarting application of investigational product. Unscheduled visits may also be necessary to repeat testing following abnormal laboratory

results, for follow-up of AEs, or for any other reason, as warranted in the judgment of the Investigator.

The following information will be collected for all subjects:

- AEs
- Concomitant medications/procedures

The following information will be collected for those subjects that had stopped study medication but are experiencing a reoccurrence of seborrheic dermatitis. These subjects may have an unscheduled visit (although an unscheduled visit is not required as subjects only need to call the site) when seborrheic dermatitis returns prior to restarting application of investigational product:

- IGA

An updated Body Diagram of seborrheic dermatitis involvement should be provided to the subject.

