3.2. Sample Size and Power

A sample size of approximately 410 subjects is planned for the study. This sample size is not based on any calculations of power or precision. This sample size will provide a sufficient population size to evaluate the long-term safety of roflumilast foam 0.3% over up to 52 weeks of treatment, and in the combination with other studies provide the development program with sufficient number of subjects to meet ICH exposure goals.

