6.1.7. Derived Variables

- **IGA success** = IGA of “completely clear” or “almost clear” plus a 2-grade improvement from Baseline. For IGA success analysis, the subjects who achieved IGA of 0 or 1 at baseline will be excluded from the analysis.
- **Erythema success** = Erythema score of 0 or 1 plus a 2-grade improvement from Baseline as observed over time. For erythema success analysis, the subjects who achieved erythema score of 0 or 1 at baseline will be excluded from the analysis.
- **Scaling success** = Scaling score of 0 or 1 plus a 2-grade improvement from Baseline as observed over time. For scaling success analysis, the subjects who achieved scaling score of 0 or 1 at baseline will be excluded from the analysis.
- **Compliance** = number of applications divided by the expected number of investigational product (IP) applications for each subject. Compliance will be calculated using drug accountability data over the entire treatment period for each subject, up to treatment completion or discontinuation.
- **Number of expected IP applications** = calculated as last treatment date - first treatment date + 1. Excluding treatment-free interval time (defined in this section).
- **Number of IP applications** = number of expected IP applications – missed IP applications as collected in the CRF. Missed IP applications will not be taken into consideration in determining number of IP applications if the reason for missing dose is per investigator confirmation of clear.

- **Days on IP** = last date of IP application – first date of IP application +1. Subjects that stop taking IP per investigator confirmation of clear will be excluded from this calculation.
- **Treatment Gap** = This will be calculated for subjects belonging to Cohort 2 Group 3 that rolled into the extension study (ARQ-154-214) with a gap. This is derived start treatment start date in ARQ-154-214 – last treatment date in ARQ-154-203 + 1.
- **Treatment Duration (weeks)** = (last date of IP application – first date of IP application +1)/7.
- **Duration of IGA success** = The date of first observation where IGA does not meet success criteria - the date of first observation of IGA success + 1. The duration of IGA success for subjects who end treatment in IGA success will be censored at the last disease assessment date. Only the first duration of IGA success will be analyzed.

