7.6. Exposure and Compliance

The number of IP applications by each subject based on diary data will be summarized using descriptive statistics appropriate for continuous variables.

The amount of IP used by each subject based on can weight will be summarized descriptively using continuous methods.

The number of days on IP will be derived as indicated in Section [6.1.7](#) and summarized descriptively.

The gap between completing study ARQ-151-203 and enrolling into this study will not be included in the above definition and will be summarized separately for subjects in Cohort 2 Group 3.

A subject will be considered compliant with the dosing regimen if the subject applies at least 80% of the expected applications during the IP application period and does not miss more than 3 consecutive doses. Doses missed due to IGA clearance were not considered as noncompliance.

AD-ST-33.06 Effective date: 12-Nov-2020

The number and percent of subjects that missed more than 3 consecutive doses will be tabulated except for subjects who withheld IP application due to IGA clear per investigator.

Investigational product application compliance will be calculated based on number of applications divided by the expected number of IP applications. Compliance will be summarized descriptively using the following categories:

- > 100%
- $\geq 80\% - \leq 100\%$
- < 80%

Drug exposure and compliance will be presented using primary and OLE baselines. The number of subjects with treatment duration (≥ 1 day, ≥ 8 weeks, ≥ 12 weeks, ≥ 24 weeks, ≥ 32 weeks, ≥ 54 weeks, and ≥ 62 weeks) will also be summarized similarly. Study duration will be summarized from primary and OLE baseline.

Similar exposure and compliance information will be summarized for subjects who completed or discontinued study before protocol amendment 1.

8. Efficacy Analysis

This study is open label without a comparator group; therefore, there will be no formal hypothesis testing performed in the study.

For the continuous variables, the number of nonmissing values and the mean, SD, minimum, Q1, Q3, median, and maximum will be tabulated by study visit; similarly, categorical variables will have the counts and proportions of each value will be tabulated by study visit.

For efficacy summaries 2 baselines will be used (primary and OLE) using Safety population as defined in Section [6.1.1](#).

All efficacy summaries for primary and OLE baselines will be presented as indicated below:

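### Treatment Duration is an elapsed span, so subjects in Groups 1, 3 and 4 who clear, stop and later restart have off-drug weeks counted as treatment in the SAP 7.6 threshold table

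*SAP*

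**What the plan says.** - **Derivation.** SAP 6.1.7 defines Treatment Duration (weeks) as "last date of IP application – first date of IP application +1)/7". No exclusion is attached.
- **Use.** SAP 7.6 plans to tabulate "The number of subjects with treatment duration (≥ 1 day, ≥ 8 weeks, ≥ 12 weeks, ≥ 24 weeks, ≥ 32 weeks", followed by 54 and 62 weeks, from both the primary and the OLE baseline. Under SAP 7 the exposure columns are Cohort 1 Group 1, Cohort 2 Groups 3 and 4, Cohort 2 Total and Overall. Cohort 1 Group 2 appears in listings only.
- **Off-drug periods.** Under Protocol 5.6.3, when the IGA is judged clear at a clinic visit, "the subject will stop applying the investigational product". Protocol 6.5 covers clearance between visits: "subject will stop application of investigational product after Investigator confirmation". In both cases the subject may restart after contacting the site when disease returns.
- **Neighbouring variables in SAP 6.1.7.** Expected applications carry the rule "Excluding treatment-free interval time (defined in this section". For Days on IP, "Subjects that stop taking IP per investigator confirmation of clear will be excluded from this calculation".
- **What SAP 7.6 does remove.** Only the gap between the parent study and this one, for Group 3, is set aside, and that is from Days on IP.
- **Purpose.** SAP 3.2 bases the sample size on no power or precision calculation. It says the sample will suffice to evaluate long-term safety and, together with other studies, "provide the development program with sufficient number of subjects to meet ICH exposure goals".

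**The concern.** Stopping when clear and restarting on recurrence is part of the regimen, so time off drug inside this study is expected. The formula sees only the first and last application dates. It gives the same answer for a subject who applied the foam daily for a year as for one who applied it for a few weeks at each end of the year.

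A reader of a row headed treatment duration ≥32 weeks will take it to mean treated for that long. In a single-arm study whose stated objective is long-term safety, this table is the most direct display of how many subjects were treated for how long. Elsewhere in the same list the SAP recognises confirmed-clear time as untreated, but nothing carries that recognition into the threshold counts.

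**Working it through.** There is no stated figure to reproduce: the documents report no exposure counts and give no distribution of off-drug time. The check applies the SAP formula to assumed dosing patterns and compares it with time actually on drug.

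**Inputs.** The formula is from SAP 6.1.7 and the thresholds from SAP 7.6. Week 52 is Day 365 (schedule, and SAP Table 3), with a visit window of 7 days either side.

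**Formulas.**
- Elapsed weeks = (last − first + 1)/7.
- On-drug weeks = (sum of days in the application periods)/7.

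**Main example (assumed): on drug Days 1-28 and 309-365.**
- Elapsed: (365 − 1 + 1)/7 = 365/7 = 52.1 weeks, counted at ≥8, ≥12, ≥24 and ≥32.
- On drug: 28 + 57 = 85 days; 85/7 = 12.1 weeks, reaching ≥8 and ≥12 only.
- Difference: 280 days, or 40 weeks, off drug.

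**Other assumed patterns.**

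| On-drug days | Elapsed weeks | On-drug weeks | Effect on row |
|---|---|---|---|
| 1-85, 309-365 | 365/7 = 52.14 | (85 + 57)/7 = 20.29 | Also counted at ≥24 and ≥32 |
| 1-29, 358-365 | 365/7 = 52.14 | (29 + 8)/7 = 5.29 | Counted up to ≥32; on-drug time reaches no row of 8 weeks or more |
| 1-84, 113-365 | 365/7 = 52.14 | (84 + 253)/7 = 48.14 | None |
| 1-85, never restarts | 85/7 = 12.14 | 85/7 = 12.14 | None |
| 1-29, 86-169, 254-365 | 365/7 = 52.14 | (29 + 84 + 112)/7 = 32.14 | None, but 20 weeks overstated |

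In the last pattern, removing only the first interval (56 days) leaves 309/7 = 44.14 weeks. The second interval (84 days) must also come out to reach 32.14.

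**How long a break must be to change a row.** For a subject whose span is the full 365 days:
- ≥32 weeks is 224 days. 365 − 224 = 141, so 142 or more days off drug are needed to lose that row.
- ≥24 weeks is 168 days. 365 − 168 = 197, so 198 or more days are needed.

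The ≥54-week row cannot be reached within this study alone, since Day 372 gives 372/7 = 53.14 weeks. It needs parent-study roflumilast time, counted from primary baseline. At the SAP Table 2 target of Day 421 (60.14 weeks), 54 weeks is 378 days and 421 − 378 = 43, so 44 days off drug already lose the row. Subjects with spans only just above a threshold are similarly sensitive to short breaks.

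**Does another provision correct this?** No. Expected applications remove the time but feed compliance. Days on IP, read literally, drops whole subjects who stop rather than the days they were off drug. The between-study gap rule does not concern clear periods inside this study.

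**The case against.** The strongest reply is that elapsed time is a legitimate measure here. A subject who follows stop-when-clear, restart-on-recurrence for a year has followed the studied regimen for a year. Adverse events are collected throughout, including while off drug, so the elapsed span fits the event window better than on-drug weeks alone. That stands, and it is why elapsed duration should be kept.

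It is also fair that actual use is visible elsewhere. SAP 7.6 summarises the number of applications and the grams used. SAP 8.2.1 reports how many subjects cleared and stopped, with a Kaplan-Meier analysis of the treatment-free interval. None of these feeds the threshold counts, so they do not show how many subjects were on drug for a given number of weeks. Nor is the different rule for expected applications a contradiction: it keeps instructed stops from being scored as missed doses.

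Three stronger readings are tempting but unsupported:
- *Intermittent users in every group are counted as long-term exposed.* Subjects who never restart are cut at their last application, many breaks change no row, and Group 2 is not tabulated.
- *Adverse event rates are diluted.* SAP 4.1 and 9.1 use numbers and percentages of subjects, and no person-time rate is planned. Changing this variable alters no adverse event percentage.
- *The ICH exposure goals would be missed.* The documents give no numerical goal, do not say whether elapsed or on-drug time counts towards it, and refer to it only in combination with other studies.

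**Conclusion.** The point holds for a defined set of subjects: those in Groups 1, 3 and 4 who are confirmed clear, stop, and later restart. Their off-drug weeks are counted as treatment. If the breaks are long enough relative to the span, they appear in a higher duration row than their on-drug time supports. For one subject the overstatement can be large (40 weeks in the main example), but the patterns used are assumptions chosen to show the mechanism. The number of subjects affected, and so the shift in any row, cannot be computed from the documents. The conclusion also assumes that the treatment duration in SAP 7.6 is the variable of that name in SAP 6.1.7; the name and the unit match. This is a matter of how exposure is labelled and displayed, and it leaves the adverse event results as they are.

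**What to change.** 1. In SAP 6.1.7 and 7.6, label the existing variable as elapsed treatment duration.
2. Add on-drug weeks = (last application date − first application date + 1 − all days off drug for investigator-confirmed clearance between a stop and a restart)/7, and tabulate it at the same thresholds and for the same groups and baselines, beside elapsed duration.
3. Subtract every such interval. SAP 6.1.7 analyses only the first treatment-free interval, which is not enough here.
4. Count the days strictly between the last application before the stop and the first after the restart (309 − 28 − 1 = 280 in the main example). The treatment-free interval formula in SAP 6.1.7 adds 1 and should not be reused unchanged.

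The cost is one extra derivation and one extra block in the exposure table. The SAP already relies on stop and restart dates and on missed doses with a clearance reason, so no new data collection should be needed, assuming those dates are held for every interval and not just the first. The downside for the sponsor is that on-drug counts at the longer thresholds will be lower than the elapsed counts wherever long breaks occurred.

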- **Duration of IGA of 0** = the date of first observation of IGA > 0 - the date of first observation of IGA of 0 and stop treatment. The duration of IGA of 0 for subjects who end treatment in IGA success will be censored at the last disease assessment date. This is for subjects who achieve IGA of 0 and stop the treatment. Subjects who achieve IGA of 0 but never stop treatment will be excluded from the analysis. For subjects who achieve IGA of 0 but stop the treatment later, the duration starts from the date of stop treatment. Only the first IGA of 0 duration will be analyzed.
- **Duration of IGA of 0 or 1** = the date of first observation of IGA > 1-the date of first observation of IGA of 0 or 1 + 1. The duration of IGA of 0 or 1 for subjects who end treatment in IGA of 0 or 1 will be censored at the last disease assessment date. Only the first IGA of 0 or 1 duration will be analyzed.
- **Disease recurrence** = the date of first observation of IGA of 2 or above after achieving IGA of 0 and stop treatment - the date of first observation of IGA of 0 + 1. Only the first disease recurrence will be analyzed.
- **Treatment-free interval** = the date of re-starting study drug due to IGA score above 0 - the date of stop treatment due to attainment of score of IGA of 0 +1, among subjects who achieve a “completely clear” IGA and stop treatment to all lesions. If subjects never re-start study drug after stopping treatment, the treatment-free interval is censored at the end of study date. Only the first treatment-free interval will be analyzed.
- **Weight of IP (g)** = dispensed can weight – returned can weight.
- **BMI (kg/m²)** = (weight in kg)/[(height in cm/100)²]. Day 1 height will be used for BMI derivation upto Week 24. For visits including week 24 through week 36, week 24 height

will be used to derive BMI. Week 52 BMI is derived using the height and weight collected at the same visit. This derivation is applied since height is not collected at all visits.

- **BMI Categories:**

- Underweight: $BMI < 18.5$
- Normal: $18.5 \leq BMI \leq 24.9$
- Overweight: $25.0 \leq BMI \leq 29.9$
- Obese: $BMI \geq 30.0$

- **WI-NRS 4-point reduction** = achievement of a 4-point reduction in WI-NRS pruritus score post-baseline compared to baseline, calculated only for subjects with a pruritus score of ≥ 4 at baseline.
- **Itch-free state** = achievement of in WI-NRS of 0 or 1.

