8.2. Secondary Efficacy Analysis

8.2.1. Investigator Global Assessment (IGA)

The IGA is an ordinal scale with five severity grades which is reported only in integers.

[Table 4](#) illustrates the description of each severity grade.

Table 4: IGA

Score	Description
0	Completely clear: No erythema, no scaling (hypo-hyperpigmentation can be present)
1	Almost clear: Residual slight erythema and/or trace amounts of scaling
2	Mild: Pink to red color and/or slight scaling
3	Moderate: Distinct redness and/or clearly visible scaling
4	Severe: Severe erythema (intense, fiery red) and/or severe scaling (coarse, thick scales with flaking onto clothes or skin)

IGA grade

IGA grade and change from baseline will be summarized using descriptive statistics at each visit by groups and overall.

The number and percentage of subjects in each IGA grade category will be summarized by cohort, group, and overall.

The number and percentage of subjects who achieve IGA 0 or 1 will be tabulated at each scheduled visit by groups and overall. In addition, the achievement of IGA of 0, the achievement of IGA success (i.e., IGA of 0 or 1 plus a 2-grade improvement from Baseline) also will be tabulated. Furthermore, 95% CIs for proportion of subjects who meet the criteria will be provided along with proportions. IGA success from OLE baseline should exclude subjects who already achieved IGA of 0 or 1 at OLE baseline.

IGA success, IGA of 0 or 1, IGA of 0 at any time post baseline including the assessments at the unscheduled visit will be summarized by groups and overall, along with 95% CIs for proportion of people who meet the criteria.

These analyses are repeated for both primary and OLE baselines. The subjects who achieved IGA of 0 or 1 at baseline will be excluded from the analysis of IGA success from baseline.

Subgroup analyses will be performed for both primary and OLE baseline for the subgroups mentioned in Section [6.1.6](#).

Duration of IGA success, Duration of IGA of 0 or 1, and Duration of IGA of 0

This analysis will be performed using IGA grade assessed in the open-label study.

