Duration of IGA success, for subjects whose IGA grade is not 0 or 1 at OLE baseline, is defined as the time from the first observation of IGA success to first subsequent time a subject's disease response does not meet the criteria for IGA Success. The duration of IGA success for subjects who end treatment in IGA success will be censored at the last disease assessment date. Only the first IGA success duration will be analyzed.

If there is no IGA assessment after the first observation of IGA success, the duration will be censored at the end of study date.

The median time (number of days) for IGA success will be analyzed using the Kaplan–Meier method. Subjects who discontinue study without relapse will be considered censored in the Kaplan–Meier analyses. The Kaplan–Meier estimate will be stratified by the IGA success time (IGA success by Week 4, between Week 4 and Week 12, between Week 12 and Week 24, between Week 24 and Week 36, and between Week 36 and Week 52).

Duration of IGA success will be summarized by Cohort, Groups, and overall.

The analysis of duration of IGA of 0 or 1 will be performed in the similar fashion.

Duration of IGA of 0 will be performed for subjects who achieve IGA of 0 post OLE baseline and stop treatment. Subjects who achieve IGA of 0 but never stop treatment will be excluded from analysis. If subject achieved IGA of 0 but stop treatment several days later, the duration

will start at the IP stop date. The analysis of duration of IGA of 0 will be in the similar fashion as the analysis for duration of IGA success.

Similar analysis from primary baseline will be performed.

Disease recurrence

This analysis will be performed using IGA assessments during the open-label study.

Time to disease recurrence is defined as time from first observation of IGA of 0 and stop treatment to first observation of IGA of 2 or higher after stop treatment. Subjects who achieve IGA of 0 but never stop treatment will be excluded from analysis. If subject achieve IGA of 0 but stop treatment several days later, the duration will start at the IP stop date. If there is other IGA assessment after achieving IGA of 0, the time to disease recurrence will be censored at the last disease assessment date. If there is no IGA assessment after the first observation of IGA success, the duration will be censored at the end of study date. The analysis of time to disease recurrence will be in the similar fashion as the analysis of duration of IGA success.

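### Duration of IGA 0: with a baseline IGA of 3 or 4, a slip to IGA 1 meets both the event rule and the censoring rule, and the SAP does not say which applies

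*SAP*

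**What the plan says.** SAP Section 6.1.7 computes the duration of IGA 0 as "the date of first observation of IGA > 0 - the date of first observation of IGA of 0 and stop treatment". The analysis set is restricted: "This is for subjects who achieve IGA of 0 and stop the treatment". Only one episode counts: "Only the first IGA of 0 duration will be analyzed". The censoring rule is "The duration of IGA of 0 for subjects who end treatment in IGA success will be censored at the last disease assessment date".

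IGA success is a different state from IGA 0. Section 8.2.1 gives it as "IGA of 0 or 1 plus a 2-grade improvement from Baseline", and Section 6.1.7 defines it the same way.

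The neighbouring definition, duration of IGA 0 or 1, ends at the first IGA above 1, and its duration "for subjects who end treatment in IGA of 0 or 1 will be censored at the last disease assessment date". There the censoring state is the state being timed. The same holds for duration of IGA success.

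Section 8.2.1 gives no separate censoring state for IGA 0. It says "The analysis of duration of IGA of 0 will be in the similar fashion as the analysis for duration of IGA success". Its general Kaplan-Meier statement is "Subjects who discontinue study without relapse will be considered censored", and relapse is not defined for the IGA 0 analysis.

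**The concern.** The event and the censoring condition should not both be able to describe one subject's outcome. Here they can, because the censoring sentence names IGA success where the neighbouring pattern would name IGA 0. It reads like wording carried over from the definition of duration of IGA success.

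If a programmer applies the sentence as written, an observed loss of clearance becomes a longer, censored time, and the Kaplan-Meier curve for clearance off treatment moves upward. If the programmer takes the first IGA above 0 as the event, it does not. The SAP presents itself as settled before any analysis, so this choice should not be left to programming.

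**Working it through.** The documents give no figure for this analysis, so there is nothing to reproduce. The check sets the two rules against each other and then works one subject through.

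**1. Where the rules overlap.** Event: IGA > 0. IGA success: IGA ≤ 1 and baseline − IGA ≥ 2. The table takes each baseline IGA against the last IGA. The last-IGA-0 column assumes that no IGA above 0 was ever seen.

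| Baseline IGA | Last IGA 0 | Last IGA 1 | Last IGA 2 |
|---|---|---|---|
| 0 or 1 | no event, not in success: no rule in 6.1.7 | event only | event only |
| 2 | censored only | event only (2 − 1 = 1 grade) | event only |
| 3 | censored only | **both** (3 − 1 = 2 grades) | event only |
| 4 | censored only | **both** (4 − 1 = 3 grades) | event only |

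The collision needs a baseline IGA of 3 or 4 and a last IGA of 1. The table also shows a small gap. A subject with baseline IGA 0 or 1 who stays clear is never in IGA success, so Section 6.1.7 gives that subject no censoring rule.

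**2. Who is exposed.**
- Primary-baseline analyses: the subgroup list in SAP Section 6.1.6 has only IGA 3 and 4 at primary baseline. One caution is that SAP Section 8 equates primary and OLE baseline for former vehicle subjects, so some of them could fall outside 3 to 4.
- De novo subjects (Cohort 2 Group 4): SAP Section 3.1 requires a baseline IGA of at least 3.
- Rollover subjects in the OLE-baseline analysis: only those whose OLE baseline IGA was 3 or 4. Section 6.1.6 allows 0 to 4 there.

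**3. One subject.** Visit days come from the SAP schedule (Table 1): Week 12 is Day 85, Week 24 is Day 169, Week 52 is Day 365. Suppose baseline IGA 3, clear and stopped on Day 85, IGA 1 at every visit from Day 169 to Day 365.
- Event rule: 169 − 85 = 84 days, event.
- Censoring sentence: 365 − 85 = 280 days, censored.

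**4. Possible size, on assumed rates only.** The documents give no transition rates. Assume everyone has baseline IGA 3 or 4, is clear and stopped on Day 85, and is seen on Days 169, 253 and 365. Let p be the chance per visit of moving from 0 to 1, and q the chance per visit of moving from 1 to 2, with no recovery.
- Losses under the event rule: 1 − (1 − p)³.
- Losses still counted if subjects ending at IGA 1 are censored: p[1 − (1 − q)²] + (1 − p)pq.

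| p, q | Event rule | Censoring sentence | Share of losses turned into censored times |
|---|---|---|---|
| 0.2, 0.1 | 1 − 0.8³ = 0.488 | 0.2×0.19 + 0.16×0.1 = 0.054 | 1 − 0.054/0.488 = 89% |
| 0.4, 0.3 | 1 − 0.6³ = 0.784 | 0.4×0.51 + 0.24×0.3 = 0.276 | 1 − 0.276/0.784 = 65% |
| 0.6, 0.5 | 1 − 0.4³ = 0.936 | 0.6×0.75 + 0.24×0.5 = 0.570 | 1 − 0.570/0.936 = 39% |

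A simulation over the same p (20 to 60%) and q (10 to 50%) added three moves. Of subjects at 0 who did not move to 1, 10% jumped to 2. Of subjects at 1 who did not move to 2, 20% returned to 0. Half of those at 2 fell back to 1. Losses were 62 to 96% under the event rule and 12 to 41% under the censoring sentence, with 56 to 87% of losses turned into censored times. The direction is the same throughout; the size depends on the assumed rates.

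**The case against.** The strongest reply is that the rest of the SAP points to the event reading. Section 10 says that the duration variables as a family now run from the first occurrence of a state to its first subsequent loss. Section 6.1.7 analyses only the first IGA 0 duration. Section 8.2.1 reserves Kaplan-Meier censoring for subjects without relapse. Usual survival practice would also date the event at the first IGA above 0 and censor only those without one.

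In addition, the neighbouring rules are not free of overlap if read literally. A subject who goes from 1 to 2 and back to 1 has lost IGA 0 or 1, yet also finishes in it. Those rules work only if the first loss takes precedence, and the same convention applied to IGA 0 would remove the collision.

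Most of this stands. It makes the event reading the more likely intention. It does not put precedence in writing, and it does not correct a censoring state that belongs to another endpoint.

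A reader might infer that the plan will inflate the duration of clearance, or that everyone who slips to IGA 1 is affected. The documents support neither inference. The first requires censoring to override an observed event, which the SAP does not say. The second ignores the two-grade condition: with a baseline IGA of 2 or less, IGA 1 is not IGA success and nothing collides.

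**Conclusion.** The point holds as a wording defect with two programmable results. The censoring state for duration of IGA 0 does not match its event, and for subjects with a baseline IGA of 3 or 4 who end at IGA 1 the two rules give different outcomes: in the worked case, an event at 84 days or censoring at 280. Any bias would run towards longer clearance off treatment, and it arises only if the censoring sentence is applied over an observed loss. How often this path occurs cannot be known from the documents; the percentages in the working rest entirely on assumed rates.

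The reach is limited. Duration of IGA 0 is planned under Secondary Efficacy Analysis in SAP Section 8.2.1, but it is not in the endpoint lists of Protocol Section 4.2.2 or SAP Sections 2.2.1.2 and 2.2.1.3. The study plans no inferential tests, and the primary safety endpoints (TEAEs and SAEs) are untouched.

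**What to change.** Replace the censoring sentence for duration of IGA 0 in SAP Section 6.1.7 with three statements:

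- Any IGA above 0 observed after stopping treatment is an event, dated at its first occurrence.
- A subject with at least one IGA assessment after stopping, and none above 0, is censored at the last disease assessment.
- A subject with no IGA assessment after stopping is handled as Section 8.2.1 handles that case for IGA success, that is, censored at the end of study date.

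The third statement is needed because a condition such as IGA 0 at every later assessment is met automatically when there are no later assessments. The new text also gives a rule for subjects with a baseline IGA of 0 or 1 who stay clear.

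Separately, add the one day (+ 1) that the formulas for duration of IGA success, duration of IGA 0 or 1, disease recurrence and treatment-free interval all include. This is a one-day consistency point and does not bear on the censoring question.

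The cost is a few lines of SAP text and one derivation specification. No data collection or sample size changes.
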